#### **7.1.2.9. Pregnancy**

If a female clinical trial participant or a female partner of a male clinical trial participant who has been exposed to the IMP becomes pregnant, the course and outcome of the pregnancy should be monitored and documented. Pregnancy is not an AE; however, the Investigator should inform the Sponsor immediately of the pregnancy by submitting a completed SAE report form (for tracking purposes) and provide any available follow up information on the Pregnancy Outcome Report Form, including perinatal and neonatal outcome. Protocol required procedures for study withdrawal must be performed on pregnant female subject unless contraindicated by pregnancy (eg, X-ray studies). Other appropriate follow-up procedures should be considered if indicated.

### 7.1.3. Laboratory Assessments

The safety laboratory assessments will be performed in accordance to the Schedule of Assessments: Table 1.

Blood samples will be collected using a standard output from the dialysis lines (Figure 2).

The safety laboratory analyses in blood will be performed at the local clinical units in EU and will be performed at a central laboratory in USA, according to their validated methods.

#### Haematology and Clinical Chemistry

- *Haematology*: Haemoglobin, haematocrit, mean corpuscular volume, mean corpuscular haemoglobin, mean corpuscular haemoglobin concentration, erythrocyte and leucocyte count and differential (absolute and percentage), and platelets
- *Clinical chemistry (serum)*: Creatinine, CK, total protein, albumin, cholesterol, LDL, HDL, triglycerides, glucose, BUN, bilirubin, sodium, potassium, calcium, phosphate, ALP, AST, ALT, and gamma-glutamyl transferase
- *Clinical chemistry (serum)*: magnesium, iron (ferritin and transferrin)
- *Heavy metals (total blood; collected in sodium heparin or EDTA (dark blue))*: zinc
- *Ionised calcium (total blood)*
- *Hb1Ac (total blood)*
- *PTH (plasma, EDTA)*: We recommend blood samples for PTH measurement should be taken into tubes containing EDTA, ideally between 10:00 and 16:00, and plasma separated within 24 h of venepuncture. Plasma samples should be stored at 4°C and analysed within 72 h of venepuncture. If plasma is not available, PTH from serum samples is also accepted.

#### Pregnancy Test

A serum pregnancy test will be performed at Screening, in female patients of childbearing potential, followed by a urine pregnancy test on a monthly basis, should urine be available.

### 7.1.4. 12-Lead Electrocardiograms

A 12-lead ECG will be obtained with the patient supine or semi-reclined and will be performed in accordance with the Schedule of Assessments (Table 1).

The Investigator will perform an overall evaluation of the ECG strips for safety purposes and the recording will be reported as “normal”, “abnormal not clinically significant (NCS)”, or “abnormal clinically significant (CS)”. Abnormalities

of clinical significance should be recorded as an AE. Cardiac intervals: PRT axis, PR, QRS, QT, RR, HR, QTcB, and QTcF will be measured.

### **Electrocardiogram Abnormalities**

As QTc prolongation is common in ESRD patients on HD and can occur due to underlying CVC disease, haemodialysis, sodium thiosulfate, calcimimetics, electrolyte disturbances (Ca, Mg and K) and overdoses of SNF472, careful QTc assessment is essential. Any QTc interval using Bazett's formula (QTcB) >500 ms or increase >60 ms from baseline in 1 or more subjects as confirmed with consecutive ECGs will be considered abnormal. It will be reported as an AE if the investigator considers it clinically relevant. Investigators should use their discretion to monitor the subject, apply appropriate management and observe until the QTcB has decreased. At the discretion of the investigator, patients with persistent QTc prolongation may be withdrawn from the trial.

#### **7.1.5. Physical Examinations**

The physical examinations will be performed in accordance with the Schedule of Assessments: Table 1.

The physical examination comprises a routine medical examination.

The routine medical examination will be recorded as "normal" or "abnormal".

#### **7.2. Haemodialysis-related Events**

The following events are known to occur during dialysis treatments:

- Hypotension
- Muscle cramps
- Disequilibrium syndrome
- Nausea and vomiting
- Headache
- Chest pain
- Itching
- Fever and chills
- Pyrogen reaction
- Hypertension

Occurrence of these events during the dialysis treatment procedure should be recorded in the CRF and indicated as haemodialysis-related events. If any of these events are considered to be unrelated to the hemodialysis treatment procedure, they should be recorded as standard adverse events.

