## 6.6. Administration of Investigational Medicinal Products

The IMP administration will consist of a single IV dose of SNF472 over a minimum of 2.5 and a maximum of 4-hour period during the patient's dialysis session. A minimum of 2.5 h of infusion is required.

The exact infusion starting and stopping times will be recorded in the CRF.

The appropriate volume of the investigational product will be administered as a constant rate IV infusion using a 100 mL bag of saline connected directly to the dialysis machine via an IV giving set, but always BEFORE the dialysis filter. The constant rate IV infusion will be carried out using an infusion pump for saline bags. SNF472 should NOT be administered directly intravenously.

The type of dialysis machine used will be documented in the CRF. The method of administration will be as follows:

[figure not shown]

Figure 2 Cartoon of the method of administration including the dialysis machine.

Any dosage interruptions will be recorded in the CRF (i.e., infusion stop and start times). In case there is an interruption of the infusion, once the infusion is re-started, the aim should be to deliver the whole dose, even if this takes longer than originally planned.

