Only clinically significant test abnormalities should be reported as AEs. Determination of the clinical significance of test abnormalities is the responsibility of the Investigator. In particular, Grade 1 or 2 haematology, chemistry, abnormalities should be carefully considered for clinical relevance by the Investigator, as they are less likely to be of clinical significance as compared to Grade 3 or Grade 4 abnormalities. Haematology and chemistry abnormalities determined to be clinically relevant will be assigned a severity rating by the Investigator. A clinical diagnosis, rather than the changes in laboratory or other assessment should be recorded on the CRF as appropriate (eg, anaemia versus low haemoglobin value, bundle branch block rather than abnormal ECG).

All AEs, including intercurrent illnesses, occurring during the clinical trial will be documented in the CRF. Concomitant illnesses that existed prior to entry into the clinical trial will not be considered AEs unless they worsen during the Treatment Period. Pre-existing conditions will be recorded in the CRF on the Medical History or appropriate page.

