#### **7.1.2.3.3. Causality**

The Investigator will assess the causality/relationship between the IMP and the AE and record that assessment in the CRF. The most likely cause of an AE/SAE (e.g., disease under treatment, concomitant disease, concomitant medication, other) will be indicated in the CRF with details of the concomitant disease, medication, or other cause.

The causal relationship of the AE to IMP will be described in terms of:

- Possible: the AE:
  - Follows a reasonable temporal sequence from administration of the IMP

- Could be reasonably explained by the patient's clinical state, environmental or toxic factors or other therapies administered to the patient
- Follows a known pattern of response to the IMP
- Unlikely: the AE:
  - Does not follow a reasonable temporal sequence from administration of the IMP
  - Could be reasonably explained by the patient's clinical state, environmental or toxic factors, or other therapies administered to the patient
  - Does not follow a known pattern of response to the IMP
  - Does not reappear or worsen upon re-challenge
- Not related:
  - The AE does not meet the above criteria
  - There is sufficient information that the aetiology of the AE is not related to the IMP

The relatedness of SAEs will also be assessed and documented on the appropriate CRF page.

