#### **7.1.2.4. Recording of Adverse Events**

Adverse events will be collected from the time a patient signs the ICF until the Follow-up Visit.

All AEs, regardless of the relationship to IMP, must be recorded in the source documents (e.g., medical record) and will be recorded on the appropriate CRF pages, and documents provided by the Sponsor.

All AE reports should contain a brief description of the event, date, and time of onset, date and time of resolution, intensity, treatment required, relationship to IMP, action taken with the IMP, outcome, and whether the event is classified as serious.

Serious adverse events should be collected for up to 30 days after the last dose of the IMP for subjects unless the subject has withdrawn consent. This could be collected as a phone call.

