### **8.2.3. Treatment Period W1-W12**

All eligible patients will receive SNF472 during their haemodialysis sessions. SNF472 will be administered at each dialysis session for the entire duration of the study. The duration of infusion of SNF472 will range from 2.5 h up to maximum time on dialysis, which would be 4 h. SNF472 should NOT be administered directly intravenously. SNF472 should NOT be administered concomitantly with STS, should STS be used. In case both drugs would be administered to the patient, the administration of SNF472 should be stopped 30 minutes before the end of the dialysis session to allow the STS infusion to take place in the last 30 minutes of the session.

In the event of Fe+ administration, the infusion of SNF472 should be stopped BEFORE starting the Fe+ infusion.

For other assessments please check Table 1.

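### Protocol 7.2 does not tie events during dialysis to the adverse event rules, so non-serious ones can be missing from the SAP's AE tables; separately, the causality grades lack a combining rule

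*Protocol*

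**What the plan says.** Protocol 7.2 lists ten event types known to occur in dialysis: hypotension, cramps, disequilibrium, nausea and vomiting, headache, chest pain, itching, fever and chills, pyrogen reaction and hypertension. The recording rule is: "Occurrence of these events during the dialysis treatment procedure should be recorded in the CRF and indicated as haemodialysis-related events". The exception follows: "If any of these events are considered to be unrelated to the hemodialysis treatment procedure, they should be recorded as standard adverse events".

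The general rules are broader. Section 7.1.2.2 says: "All AEs, including intercurrent illnesses, occurring during the clinical trial will be documented in the CRF". Section 7.1.2.4 says: "All AEs, regardless of the relationship to IMP, must be recorded in the source documents", and requires each AE report to state the relationship to the study drug. Section 7.1.2.3.3 says: "The Investigator will assess the causality/relationship between the IMP and the AE and record that assessment in the CRF".

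On exposure, section 8.2.3 says: "SNF472 will be administered at each dialysis session for the entire duration of the study", and "The duration of infusion of SNF472 will range from 2.5 h up to maximum time on dialysis, which would be 4 h".

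SAP 9.3.1 tabulates AEs, including by relationship to SNF472. The SAP does not mention haemodialysis-related events.

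Protocol 7.1.2.3.3 defines *Possible* with three bullets, *Unlikely* with four and *Not related* with two. Nothing says whether all or any bullets must be met.

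**The concern.** The default in 7.2 attributes a listed event to dialysis whenever it occurs during dialysis. In this trial the drug is given only during dialysis, so timing within a session does not separate the two causes, and a link to dialysis does not rule out a contribution from SNF472. Contrasting these events with standard adverse events suggests that they may be kept outside the AE data. If they are, they get no SNF472 grade under 7.2 and enter no table in SAP 9.3.1.

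Safety is part of the objective in SAP 5.1, and there is no control arm to show the background rate of these events. SAP 8.6 expects one or two subjects per site across three countries. If sites read 7.2 or the causality bullets differently, the same event can be recorded or graded differently, and that could not be told apart from differences between patients.

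**Working it through.** The documents give no figure to reproduce. The check is textual, with an enumeration of the causality rule.

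**1. What happens to a listed, non-serious event during infusion**

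| Reading of the mark in 7.2 | SNF472 relationship graded? | In SAP 9.3.1 tables? |
|---|---|---|
| Flag on an AE | Yes, through 7.1.2.3.3 and 7.1.2.4 | Yes; loss is zero |
| Separate category | Not asked for in 7.2 | No; listings only (SAP 8.1) |

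Sections 7.1.2 and 7.2 do not refer to each other, so the text does not choose between the rows.

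**2. How far infusion and dialysis overlap** (Protocol 8.2.3, 4 h session)

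- Shortest infusion: 2.5/4 = 62.5% of the session. Longest: 4/4 = 100%.
- If sodium thiosulfate takes the last 30 minutes: at most (4 − 0.5)/4 = 87.5%.
- Section 6.6 says: "The exact infusion starting and stopping times will be recorded in the CRF". Some events can therefore be placed outside dosing, but not those that begin during the infusion.
- Planned sessions: 36 × 15 completers = 540. The number dosed is not fixed, since Protocol 5.1 allows replacement and SAP 6.1 says up to 15. An assumed 12 to 18 full courses gives 36 × 12 = 432 to 36 × 18 = 648.

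These figures measure exposure. They are not counts of lost events.

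**3. Causality bullets**

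Let T = reasonable timing, A = another cause could explain the event, K = known pattern of response. Leave re-challenge out at first. *Possible* uses {T, A, K}; *Unlikely* uses {not T, A, not K}. There are 2³ = 8 combinations.

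| T | A | K | All bullets required | Any bullet suffices |
|---|---|---|---|---|
| 1 | 1 | 1 | Possible | both |
| 1 | 1 | 0 | neither | both |
| 1 | 0 | 1 | neither | Possible only |
| 1 | 0 | 0 | neither | both |
| 0 | 1 | 1 | neither | both |
| 0 | 1 | 0 | Unlikely | both |
| 0 | 0 | 1 | neither | both |
| 0 | 0 | 0 | neither | Unlikely only |

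- All required: 1 *Possible*, 1 *Unlikely*, 6 neither. The single *Possible* row is one where another cause could explain the event.
- Any suffices: 1 *Possible* only, 1 *Unlikely* only, 6 both.
- With re-challenge added (2⁴ = 16): all required gives 2 *Possible*, 1 *Unlikely*, 13 neither; any suffices gives 1 *Possible* only, 2 *Unlikely* only, 13 both.

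**4. Where T = 1, A = 0, K = 1 ends up.** If all bullets are required, the event is neither *Possible* nor *Unlikely*. It meets the first bullet of *Not related* (the criteria above are not met). It fails the second, which needs sufficient information that the aetiology lies elsewhere. It therefore has no grade. If any bullet suffices, and re-challenge is left out, it is *Possible* only.

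The counts show that the wording is ambiguous. They are not event frequencies or an error rate.

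**The case against.** The strongest case is that the mark is only an attribute of an AE. The AE definition in 7.1.2.2 makes no exemption for dialysis, 7.1.2.4 requires relationship to the study drug in every AE report, and 7.1.2.3.3 already has the most likely cause of an AE marked in the CRF. On that reading 7.2 need not ask about SNF472 again. Calling the other events standard may also just mean that the dialysis events are a subtype of AE. This stands as a fair reading, and on it no event is lost. What remains is that 7.2 does not say so, and the SAP has no output showing the flag.

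There are also safeguards. All SAEs are reported within 24 hours whatever the causality (7.1.2.5), an independent monitor reviews all the safety information collected (7.1.2.8), and data are in general listed (SAP 8.1). ECG and ionised calcium measurements do not pass through 7.2. These limit the point to non-serious events in summary tables. They do not supply an SNF472 grade that was never requested.

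Headache is the only listed type that Phase 1 also named as possibly related, and Protocol 2.3.2 says those effects were not seen in haemodialysis patients. That is fair, and nothing here claims that SNF472 causes the listed events.

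**Conclusion.** The point holds in a limited form. Protocol 7.2 is at best not linked to the AE rules and at worst in conflict with them, and SAP 9.3.1 has no output for the events it marks. Non-serious events during infusion can therefore be missing from the AE and relationship tables. The size of the effect cannot be estimated: no event rate is given, and the loss is zero on the flag reading.

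The causality scale fails on either consistent reading. If all bullets are required, an event with good timing, a known pattern and no other cause has no grade. If any bullet suffices, 6 of 8 combinations get two grades.

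A reader might infer two stronger claims that the documents do not support. The first is that events are in fact left out of the tables; without the CRF and shells, this is only possible. The second is that the well-timed event with no other cause falls into *Not related*. That would need all bullets for *Possible* but any bullet for *Not related*, which mixes two readings.

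Severity is minor to moderate.

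**What to change.** 1. **Protocol 7.2:** state that the haemodialysis mark is a flag on an AE, that 7.1.2 applies in full, and that relationship to SNF472 and relationship to dialysis are assessed separately.
2. **SAP 9.3.1:** add a table of haemodialysis-flagged events by preferred term, and a combined table of AEs and haemodialysis-related events counting each event once. Where events were already recorded without an SNF472 grade, the combined table restores them to the overall AE counts but not to the relationship table. Show them there as not assessed.
3. **Protocol 7.1.2.3.3:** state how the bullets combine within each grade, and that the absence of an alternative cause does not prevent *Possible*.

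The cost is two SAP tables, coding of the ten event types if not already done, and a short protocol and CRF clarification. Reported AE counts will rise, and some added events will be ordinary dialysis effects; the separate dialysis grade keeps them identifiable. The number of added entries is unknown. At assumed rates of 1%, 5% and 10% of 540 sessions it would be 5.4, 27 and 54, each with two relationship grades.

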### 7.3. Pharmacokinetic and Pharmacodynamic Parameters

#### 7.3.1. Pharmacokinetic and Pharmacodynamic Blood Sample Collection and Handling

Blood samples for PK and PD analyses of SNF472 will be collected according to the Schedule of Assessments (Table 1).

See separate laboratory manual instructions for detailed description of PK and PD sample collection.

The actual date and time of each blood sample collected will be recorded.

Blood samples will be collected using one of the lines already connected to the patient (Figure 2).

Approximately, 4 mL of blood at pre-dose and 4 mL of blood at end of infusion will be collected into polyethylene terephthalate (Vacutainer) tubes containing potassium (K3) EDTA. Samples will be divided into aliquots for PK and PD sampling according to the laboratory manual instructions.

Tubes will be labelled with the following minimum information: clinical study number, Patient ID, sample type, day and time, primary or back-up sample (see sample label, Figure 3).

Figure 3 Cryovial sample labels for sample collections

**SNFCT2015-04**  
**PK Plasma**  
**Primary**

Visit: \_\_\_\_\_  
Timepoint: \_\_\_\_\_  
Sub. N°: \_\_\_\_\_  
Col. time: |\_|\_| : |\_|\_|  
          H H M M

All samples will immediately be placed on crushed ice and centrifuged (1900g for 10 minutes at 4°C) within 30 minutes of collection. The resultant plasma for each time-point will be divided into aliquots according to the laboratory manual instructions and transferred into appropriately labelled PET tubes (e.g., 1.8 mL storage cryovials). Plasma samples should be kept on dry ice at the site until courier collection. Samples will be stored at -80°C.

Samples for GLP PK analysis will be packed on dry ice and shipped by courier to the [REDACTED] depot for storage in Europe:

[REDACTED]  
[REDACTED]  
[REDACTED]  
[REDACTED]  
[REDACTED]  
[REDACTED]  
[REDACTED]  
[REDACTED]

Samples for GLP PK analysis will be packed on dry ice and shipped by courier [REDACTED]  
[REDACTED]:

[REDACTED]  
[REDACTED]  
[REDACTED]

[REDACTED]  
[REDACTED]  
[REDACTED]  
[REDACTED]  
[REDACTED]  
[REDACTED]

[REDACTED]

[REDACTED]

### 7.3.2. Pharmacokinetic Variables

The following PK parameter will be assessed for SNF472:

$C_{max}$  Maximum observed plasma concentration

### 7.4. Biomarkers

Blood samples for biomarker (BK) analysis will be collected according to the Schedule of Assessments: Table 1. Biomarkers will be defined and analysed at the end of the study.

The actual date and time of each blood sample collected will be recorded.

The 2 mL blood sample at pre-dose and end of infusion (in duplicate = 4 ml) will be collected into serum-separating gel PET tubes (Vacutainer) to obtain serum (as described in Table 1). All samples will be then centrifuged (1500g for 10 minutes). The resultant serum for each time-point (in duplicate) will be divided into 2 aliquots (250 µL serum per aliquot each for Aliquot 1/2 and Aliquot 2/2) and transferred to 2 appropriately labelled PET tubes (e.g., 1.8 mL storage cryovials). Samples stored at -80°C.

Serum samples for biomarker analysis will be packed on dry ice and shipped by courier at the end of the study (single shipment) to in Europe:

[REDACTED]

[REDACTED]

[REDACTED]

[REDACTED]

### 7.5. Scores and Evaluations

Several different scores and evaluations will be performed throughout the study (see Table 1).

The assessment of the degree of pain a patient feels will be measured with the VAS.

To assess the course of healing of the ulcers, the Bates Jensen Wound Assessment Tool will be used. Of note, elements of the Bates-Jensen Wound Assessment tool which imply probing the wound or measuring its depth are left to the discretion of the treating physician at the site and are not compulsory.

Quality of life will be assessed with the Wound QoL score.

Images of the primary, secondary, and tertiary wounds will be taken at regular intervals and uploaded into the clinical database.

### 7.5.1. Pain Score -VAS

The Visual Analogue Scale (VAS) will be used to assess pain, as per the patient. A VAS is a measurement instrument that aims to measure a characteristic or attitude that is believed to range across a continuum of values and cannot easily be directly measured. For example, the amount of pain that a patient feels ranges across a continuum from none to an extreme amount of pain.

Operationally, a VAS is usually a horizontal line, 100 mm in length, anchored by word descriptors at each end, as illustrated in

[figure not shown]

Figure 4 The patient marks on the line the point that he feels represents his perception of his current status. The VAS score is determined by measuring in millimetres from the left hand end of the line to the point that the patient marks [51].

[figure not shown]

Figure 4: VAS Analogue Scale

#### 7.5.2. Lesion Score – Bates-Jensen Wound Assessment Tool

The site investigator will use the Bates Jensen Wound Assessment Tool (BWAT) to assess the course of the lesion. BWAT is a measuring instrument used to assess and monitor healing in pressure ulcers and other chronic wounds[49]. It is not, however, specific for CUA. It uses a numerical scale to rate wound characteristics from best to worst possible. It consists of 15 items, two of which (location and shape) are not scored. Scored items are:

- Size
- Depth
- Edges
- Undermining or pockets
- Necrotic tissue type
- Necrotic tissue amount
- Exudate type
- Exudate amount
- Surrounding skin colour
- Peripheral tissue oedema
- Peripheral tissue induration
- Granulation tissue
- Epithelialization

Each item should be scored from 1 to 5, with 1 being the best for that attribute.

Of note, elements of the Bates-Jensen Wound Assessment tool which imply probing the wound or measuring its depth are left to the discretion of the treating physician at the site and are not compulsory. The BJWAT total score will be calculated using a standard methodology for any missing values. Additionally, scores for the component items will be assessed longitudinally. Improvement or worsening will be assessed in the total score and the individual component scores.

